### **Duration of ICU stay (Actual and Medical Equivalence)**

The duration (number of days) of ICU stay from post-randomization through Day 29 will be calculated based on ICU admission and discharge (actual and medical equivalence) dates recorded on the eCRF. Number of days in the ICU will be compared between treatment groups using an ANOVA model, including number of days in the ICU as a dependent variable and treatment group as a fixed effect. From this model, the LS means and 95% CIs for each treatment group, the treatment difference in the LS means, the 95% CI for the difference, and the associated p-value will be presented. If appropriate, an ANCOVA model may instead be used to additionally adjust for baseline characteristics such as age and gender.

Subjects who died while in the ICU will be assigned as in the ICU for the number of days remaining from the day of death to Day 29 for the analysis. Subjects who were at ICU at study completion will be assigned an ICU end date equals to the date of completion for the purpose of deriving the number of ICU days.

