#### **4.4 Handling of Dropouts or Missing Data**

Missing data will be treated as missing and no method for imputation is planned for study population or safety analyses except for the partial end dates/times for concomitant medications (Section 5.6) and partial onset dates/times for AEs (Section 7.2.1). When applicable, missing data for binary and selected continuous efficacy endpoints will be imputed using a most conservative/worst case approach, and the related details are described in Section 6.

Time to event endpoints will have events coded as right censored or competing events per the

following table:

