#### 4.6 Data Derivations and Transformations

The following derivations will be used in this study:

Study Day:

- Date of assessment – date of randomization + 1 for assessments done on or after date of randomization
- Date of assessment – date of randomization for assessments done before date of randomization

Baseline Observation: the last non-missing value prior to randomization.

Duration:

- Duration in days = end date – start date + 1
- Duration in minutes = end time in minutes – start time in minutes

Origin or Start Date for Time to Event Endpoints:

- Time to death: date of randomization
- Time to ICU Discharge (actual and medical equivalence, if applicable): date of randomization or date of ICU admission, whichever was later
- Time to Hospital Discharge (actual and medical equivalence, if applicable): date of randomization
- Time to Clinical Response: date of randomization

Event Date for Time to Clinical Response:

- If a subject met the criteria for clinical response at multiple assessments, the date of the first assessment meeting the definition of clinical response will be used as the event date for deriving time to clinical response.

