### **Duration of Hospitalization (Actual and Medical Equivalence)**

The duration (number of days) of hospitalization from post-randomization through Day 29 will be calculated based on hospital admission and discharge (actual and medical equivalence) dates recorded on the eCRF. Number of days in the hospital will be compared between treatment groups using an ANOVA model, including number of days in the hospital as a dependent variable and treatment group as a fixed effect. From this model, the LS means and 95% CIs for each treatment group, the treatment difference in the LS means, the 95% CI for the difference, and the associated p-value will be presented. If appropriate, an ANCOVA model may instead be used to additionally adjust for baseline characteristics such as age and gender.

Subjects who died while in the hospital will be assigned as in the hospital for the number of days remaining from the day of death to Day 29 for the analysis. Subjects who were in the hospital at study completion will be assigned a hospitalization end date equals to the date of completion for the purpose of deriving the duration of hospitalization.

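### The ICU-days analysis carries a death to Day 29 only if it happens in the ICU, so a subject who leaves the ICU and then dies scores like a survivor discharged that day.

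*SAP*

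**What the plan says.** SAP 6.2, Duration of ICU stay, takes the number of ICU days after randomization through Day 29, "calculated based on ICU admission and discharge (actual and medical equivalence) dates recorded on the eCRF". Two rules modify the count. The rule for deaths, which runs up to Day 29, is "Subjects who died while in the ICU will be assigned as in the ICU for the number of days remaining". The rule for those still there at the end is "Subjects who were at ICU at study completion will be assigned an ICU end date equals to the date of completion". The analysis is then "Number of days in the ICU will be compared between treatment groups using an ANOVA model", with an optional adjustment for baseline characteristics.

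SAP 6.2, Duration of Hospitalization, has the parallel rule, again up to Day 29: "Subjects who died while in the hospital will be assigned as in the hospital for the number of days remaining". For ventilation days and oxygen days, the extension to Day 29 applies to a death during hospitalization with no stop date on the eCRF.

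SAP 4.4 says that, when applicable, "missing data for binary and selected continuous efficacy endpoints will be imputed using a most conservative/worst case approach", with details left to Section 6. SAP 4.6 gives "Duration in days = end date – start date + 1".

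**The concern.** All four duration analyses extend certain deaths to Day 29, so the SAP has chosen to score death as the worst result rather than as a short stay. For ICU days that choice depends on where the subject died. A subject stepped down to the ward who then dies keeps the stay up to ICU discharge, and the death adds nothing.

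Two consequences follow.

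- **Dilution.** If one arm truly has fewer deaths, the deaths scored as short stays shrink the ICU-days difference, even when the share of deaths after ICU discharge is the same in both arms.
- **Place-of-death bias.** If that share differs between arms, ICU days can differ with no difference in mortality or in survivors' stays. Transfer out of the ICU involves staff judgement, and staff know the assigned treatment in this open-label trial.

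**Working it through.** The plan states no power, SD, effect size or mortality rate for this endpoint, so there is no figure to reproduce.

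**1. Does any other text close the gap?**
- SAP 4.4 imputes missing data. A recorded ICU discharge date is not missing.
- SAP Table 1 covers time-to-event endpoints only.
- SAP 4.6 gives a formula and no rule for deaths.
- In the analysis of time to ICU discharge, only deaths before discharge compete. A later death leaves the discharge event in place.

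**2. Scores under the rule** (SAP 4.6 formula, ICU start on Day 1):

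| Subject | SAP rule | All deaths carried to Day 29 |
|---|---|---|
| Survivor, leaves ICU Day 8 | 8 | 8 |
| Leaves ICU Day 8, dies on ward Day 12 | 8 | 29 |
| Dies in ICU Day 12 | 29 | 29 |
| Leaves ICU Day 20, dies Day 25 | 20 | 29 |
| Alive in ICU at Day 29 | 29 | 29 |

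The two Day-12 deaths differ by 29 - 8 = 21 days through place of death alone. A late discharge gains less.

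**3. Shift in one arm's mean.** With k post-ICU deaths, discharge on day d and about 50 per arm (SAP 9: about 100 subjects, randomized 1:1), the mean is understated by k x (29 - d)/50. Per death this is 0.48, 0.42, 0.34 or 0.18 days for d = 5, 8, 12 or 20. Assume mortality of 20-40%, 5-30% of deaths after ICU discharge, and d from 5 to 20. Then k runs from 50 x 0.20 x 0.05 = 0.5 to 50 x 0.40 x 0.30 = 6, and the understatement from 0.5 x 9/50 = 0.09 to 6 x 24/50 = 2.88 days.

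**4. Effect on the comparison** (d = 8 in both arms):
- Dilution with 40% v 20% mortality and a common post-ICU share s: the difference shrinks by s x 0.20 x 21, which is 0.84 days at s = 20% and 1.68 days at s = 40%.
- Bias with 35% mortality in both arms and shares of 10% v 40%: 0.35 x 0.30 x 21 = 2.2 days. At 10% v 20%: 0.35 x 0.10 x 21 = 0.7 days.
- Single constructed trial, 15 deaths per arm and identical survivors: 3 v 0 post-ICU deaths gives -3 x 21/50 = -1.26 days (ANOVA p = 0.47), and 5 v 0 gives -2.10 days (p = 0.22). Carrying all deaths gives 0.

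**5. Simulation.** Assumptions: 50 per arm, stays lognormal with log-SD 0.5-0.9 and capped at Day 29, two-sided 5% test of means. Median survivor stay is 10 v 8 days for power and 9 days in both arms for false positives. The ranges cover that spread, and ICU discharge of subjects who later die from about Day 6-7 up to the same timing as survivors.

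| Scenario | Result |
|---|---|
| 40% v 20% mortality, all deaths carried | power about 62-80% |
| Same, 20% of deaths after ICU discharge | about 49-72% |
| Same, 40% of deaths after ICU discharge | about 35-67% |
| 35% mortality in both arms, equal post-ICU shares | false positives about 5% |
| Same, 10% v 20% post-ICU | 6-8% |
| Same, 10% v 25% | 7-10% |
| Same, 10% v 40% | 14-23% |

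If subjects who later die leave the ICU around Day 15 instead, the 10% v 40% case falls to about 10-12%. Carrying all deaths returns the rate to about 5%.

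**The case against.** - **These deaths are visible elsewhere.** This stands. The primary analysis counts every death through Day 29, the ordinal scale puts death in its worst category wherever it occurs, and a ward death is carried to Day 29 in hospital days. A reader might infer that the hospital-days analysis has the same fault for ward deaths, or that the mortality result is affected. The text supports neither. The hospital-days gap is confined to deaths after hospital discharge and to the medical-equivalence version.
- **It is a supporting analysis.** This also stands. The listed endpoint is time to ICU discharge, analysed by cumulative incidence and Gray's test. The ICU-days ANOVA was added in SAP version 2.0, and the trial is an exploratory pilot without multiplicity adjustment. Still, duration of ICU stay is named in the secondary objective, and the ANOVA reports a p-value.
- **Five days in the ICU are five days, so this is a choice of estimand.** This would hold for a pure resource-use count. But the SAP already adds days that subjects who die in the ICU never spent there. Having made death part of the score, it applies the penalty by location.
- **The size is scenario-driven.** Correct. A reader might take the 14-23% as the expected error rate. It needs a large imbalance in place of death and fairly early ICU discharge of those who die, and the documents give no reason to expect either. Much of the lost power also concerns a mortality difference that the primary endpoint tests directly.

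**Conclusion.** The rule is wrong as written, on a secondary analysis. A death by Day 29 after ICU discharge is scored as a survivor's discharge, against the SAP's own decision to penalise death, and nothing else in the SAP corrects it. Confidence is high about the gap and low about its size. Dilution of a real mortality benefit needs only that some deaths follow ICU discharge. A false difference needs post-ICU deaths to differ between arms in number or timing; with equal shares and timing the test keeps its 5% level. Open-label treatment makes such a difference possible, but nothing in the documents shows that it would occur.

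The medical-equivalence version is less clear still. The SAP does not say how to score a subject who met equivalence, deteriorated, and died while still physically in the ICU or hospital.

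**What to change.** In SAP 6.2, replace the two sentences on deaths with: 'Any subject who dies on or before Day 29, in any location, is assigned ICU days (and hospital days) from the day of ICU (or hospital) discharge or death, whichever is earlier, through Day 29.' Count the day of discharge or death once. State that the rule applies to both the actual and the medical-equivalence versions, with the equivalence date taking the place of discharge in the latter.

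For consistency, apply the same all-deaths rule to ventilation days and oxygen days, where the extension now requires an in-hospital death without a recorded stop date.

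The cost is one sentence per endpoint and a small programming change. Time to death is already derived (SAP 4.6), so no new data are needed. The change should be made before the data are analysed, because a later change in an open-label trial would look data-driven.

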### **Duration of mechanical ventilation**

The duration (number of days) on mechanical ventilation from post randomization through Day 29 will be calculated based on the start/stop dates of mechanical ventilation recorded on the eCRF All Visits page “General Duration of Hospitalization, & Overall Requirement for Mechanical Ventilation, ICU Admission and/or Oxygen Supplementation”. Number of days on mechanical ventilation will be compared between treatment groups using an ANOVA model, including number of days on mechanical ventilation as a dependent variable and treatment group as a fixed effect. From this model, the LS means and 95% CIs for each treatment group, the treatment difference in the LS means, the 95% CI for the difference, and the associated p-value will be presented. If appropriate, an ANCOVA model may instead be used to additionally adjust for baseline characteristics such as age and gender.

Subjects who died during the hospitalization without a stop date of mechanical ventilation recorded on the eCRF will be assigned as being on mechanical ventilation for the number of days remaining to Day 29 for the analysis. Subjects who had mechanical ventilation ongoing at study completion will be assigned a mechanical ventilation end date equals to the date of completion for the purpose of deriving duration of mechanical ventilation. Subjects who are never placed on mechanical ventilation through Day 29 will be included in the analysis with a value of zero days on mechanical ventilation.

A listing of all mechanical ventilation and oxygen administration data collected throughout the study will be provided.

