## 4. GENERAL CONSIDERATIONS FOR DATA ANALYSIS

Unless otherwise specified, continuous variables will be summarized using descriptive statistics (n, mean, standard deviation, median, minimum, and maximum). Categorical variables will be summarized showing the number and percentage of subjects within each category.

Summary results will be provided for each treatment group. All tabulations will be based on pooled data across centers.

All statistical tests will be two-sided and tested at the 5% level of significance.

Analyses will be performed using SAS for Windows statistical software, version 9.4 or higher (SAS, Cary, NC), except where other software may be deemed more appropriate. In the event that other software is used to perform some analyses, the details will be provided in the Clinical Study Report.

■ will perform all efficacy and safety analyses described in this SAP.

Subject data will be listed, sorted by treatment group and subject number. When applicable, listings will be additionally sorted by visit and assessment date/time.

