### **Duration of any oxygen use**

The duration (number of Days) of any oxygen use from Day 1 through Day 29 will be calculated based on the start/stop date of using oxygen supplementation recorded on the eCRF All Visits page "General Duration of Hospitalization, & Overall Requirement for Mechanical Ventilation, ICU Admission and/or Oxygen Supplementation". Number of days on oxygen will be compared between treatment groups using an analysis of variance (ANOVA) model, including number of days on oxygen as a dependent variable and treatment group as a fixed effect. From this model, the LS means and 95% CIs for each treatment group, the treatment difference in the LS means, the 95% CI for the difference, and the associated p-value will be presented. If appropriate, an analysis of covariance (ANCOVA) model may instead be used to additionally adjust for baseline characteristics such as age and gender.

Subjects who died during the hospitalization without a stop date of using oxygen supplementation recorded on the eCRF will be assigned as being on oxygen for the number of days remaining to Day 29 for the analysis. Subjects who had oxygen use ongoing at study completion will be assigned an oxygen use end date equals to the date of completion for the purpose of deriving duration of oxygen use. Subjects who never received supplemental oxygen through Day 29 will be included in the analysis with a value of zero days of oxygen use.

A listing of all supplemental oxygen and saturation ( $SpO_2$  and  $SaO_2$ ) data collected throughout the study will be provided.

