### **Ordinal scales**

- a) The absolute value and change from baseline in the Ordinal scale from Day 1 through Day

29 will be summarized by treatment group and visit using descriptive statistics.

Mean change in Ordinal scales through Day 29 will be evaluated by fitting a linear mixed-effects model for repeated measures (MMRM). The model will include change from baseline in Ordinal scale as the repeated dependent variable; treatment (as a class variable), visit (as a class variable), and treatment-by-visit interaction as fixed effects; baseline Ordinal scale, age and gender as covariates; and measures within subject at each visit as a repeated measure. An unstructured covariance matrix will be used to model the within-subject error. If the fit of the unstructured covariance structure fails to converge, a compound symmetry covariance structure will be used. Parameters will be estimated using restricted maximum likelihood with the Kenward-Roger method for calculating the denominator degrees of freedom. Data collected starting at the Day 2 visit and up to the Day 29 visit will be included in this analysis. Missing data will not be imputed. From this model, the least-squares (LS) means and 95% CIs for each treatment group, the treatment difference in the LS means, the 95% CI for the difference, and the associated p-value will be reported on Days 15 and 29, as well as for the average across all post-baseline visits.

- b) The proportion of subjects in each severity category of the 7-point Ordinal scale at Day 15 and Day 29 will be tabulated. The difference in severity category distribution between treatment groups at Day 15 and Day 29 will be examined using proportional-odds cumulative logit model. The cumulative logits model will compare lower ordinal scales to higher ones, or equivalently, less favorable outcomes to more favorable ones. The model may be adjusted for baseline characteristics such as age and gender, if appropriate. The estimated odds ratio and 95% CI will be presented. Graphical illustrations of the fitted model will also be presented for Day 15 and Day 29.

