### **9. SAMPLE SIZE AND POWER CALCULATIONS**

Because of the urgency and lack of previous prospective COVID-19 data, sample size estimation remains incompletely defined; however the size of this pilot study is commensurate with other Phase 2 investigations ongoing during the COVID-19 pandemic. Approximately 100 subjects are allowed to be randomized as part of a humanitarian effort against COVID-19.

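### The ICU, ventilation, hospital and oxygen day counts are compared by a treatment-only ANOVA that is valid but leaves the recorded baseline level of respiratory support unused; a prespecified ANCOVA would be a small, nearly free gain in precision

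*SAP*

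**What the plan says.** SAP 6.2 uses the same model for each duration endpoint. For ICU stay it is an ANOVA "including number of days in the ICU as a dependent variable and treatment group as a fixed effect", for hospitalization "including number of days in the hospital as a dependent variable and treatment group as a fixed effect" and for oxygen "including number of days on oxygen as a dependent variable and treatment group as a fixed effect". Ventilation days are handled the same way. ICU and hospital stay are each analysed twice (actual and medical equivalence), so six comparisons are affected.

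Each of these subsections ends with the same option: "If appropriate, an ANCOVA model may instead be used to additionally adjust for baseline characteristics such as age and gender". It does not say what makes adjustment appropriate, who decides, or when.

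Other parts of the documents bear on this:

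- Inclusion criterion 3b (Protocol 5.1) admits subjects on mechanical ventilation together with subjects on supplemental oxygen only.
- Protocol 4.3.2 describes one central list used in order and mentions no stratification factor.
- Protocol 7.2.2 and Appendix 1 record the Ordinal scale, oxygen use and ventilation at Screening/Baseline, and randomisation follows only when those assessments are complete.
- SAP 4.6 defines baseline as the last non-missing value before randomisation.
- The repeated-measures model for the Ordinal scale has "baseline Ordinal scale, age and gender as covariates".
- For ICU and hospital stay, SAP 6.2 also plans cumulative incidence functions with death as a competing event, compared by Gray's test.

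**The concern.** A subject already ventilated at randomisation starts to accrue ventilator days at once, while one who is never ventilated scores zero. The starting level of support is therefore a likely predictor of later support days, most directly for ventilation. With that variable left out, the variation it explains stays in the residual, and the standard error is larger than it need be. With no stratification described, a chance difference between arms in the share ventilated at entry also passes uncorrected into the estimated difference.

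The optional wording adds a second issue. In an open-label trial, a reader of the SAP cannot tell which of two models is the planned one.

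**Working it through.** **Stated figures.** The SAP gives the test level ("All statistical tests will be two-sided and tested at the 5% level of significance") and the size ("Approximately 100 subjects are allowed to be randomized as part of a humanitarian effort against COVID-19"), so about 50 per arm. It gives no power, effect size or SD: "sample size estimation remains incompletely defined". There is no planned figure to reproduce, and every input below other than n and alpha is an assumption.

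**1. Precision as a function of R².** Let R² be the share of variance in days explained by the baseline covariate. The residual SD is SD × √(1 − R²), and the number of unadjusted subjects that matches 100 adjusted subjects is 100/(1 − R²).

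With 50 per arm, unadjusted power reaches 80% at (1.960 + 0.842) × √(2/50) = 0.56 SD. For a true difference of 0.4 SD, power is Φ(0.4/[√(1 − R²) × √(2/50)] − 1.96).

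| R² | Equivalent unadjusted N | Power for 0.4 SD |
|---|---|---|
| 0 | 100 | 52% |
| 0.03 | 103 | 53% |
| 0.10 | 111 | 56% |
| 0.20 | 125 | 61% |
| 0.30 | 143 | 67% |
| 0.34 | 152 | 69% |

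**2. Plausible R² for ventilator days.** Days were simulated from 0 to 29, with exponential durations (median 10 days) and deaths set to 29 as a simplified form of the SAP's rule. The inputs varied were the share ventilated at entry, Day 29 mortality (ventilated versus not), and the chance that a non-ventilated subject is ventilated later.

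| Ventilated at entry | Mortality | Later ventilated | R² |
|---|---|---|---|
| 20% | 35% vs 30% | 50% | 0.03 |
| 35% | 40% vs 25% | 50% | 0.08 |
| 20% | 50% vs 20% | 30% | 0.15 |
| 35% | 50% vs 20% | 30% | 0.20 |
| 35% | 60% vs 15% | 20% | 0.34 |

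In 3,000 simulated trials per scenario (the last four rows, and 50% ventilated with the inputs of the third and fourth), type I error was 4.7-5.8% with either model. Both estimators averaged close to zero under the null. Under an assumed 30% effect, adjustment raised power by about 3 to 8 points, for example from 28.3% to 33.4% (R² about 0.20) and from 22.9% to 30.4% (R² about 0.32).

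**3. Hospital and oxygen days.** Every entrant needs ventilation and/or oxygen, and in-hospital deaths are filled to Day 29, so baseline ventilation separates subjects less sharply. Assumed median stays of 20 versus 13 days (hospital) and 17 versus 11 days (oxygen), ventilated versus not, gave R² of about 0.04 to 0.17, and another set of inputs gave 0.03 to 0.14 for hospital days. A range of 0.03 to 0.17 is worth 1/(1 − 0.03) to 1/(1 − 0.17), or about 3% to 20% more subjects. These are not bounds: R² is lower still if mortality hardly differs by baseline ventilation.

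**4. Chance imbalance.** Under simple randomisation with 50 per arm, the ventilated counts are two independent Binomial(50, p) variables. The exact probability that they differ by 5 or more (10 points) is 26% at p = 20% and 36% at p = 40% or 60%, peaking just under 37% at p = 50%. If ventilated and non-ventilated subjects differ by 5, 10 or 15 mean days, a 10-point gap moves the unadjusted difference by 0.10 × 5, 10 or 15 = 0.5, 1.0 or 1.5 days. The SD of the unadjusted estimate under the null was 2.50-2.65 days in the simulations, so the shift is smaller than one standard error.

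**The case against.** - **The ANOVA is a valid analysis.** A reader might infer that the treatment-only model is biased. It is not: chance imbalance is ordinary sampling variation already reflected in its standard error, type I error is held, and the estimate is unbiased over randomisations. This stands. What is lost is precision, and correction in the trial as realised.
- **The SAP already allows adjustment.** Protocol 9.1 lists ANCOVA, and the SAP's list of covariates is open-ended, so baseline support could be added. True, but nothing commits to it. A reader might also infer that the model will be chosen after the results are seen. The SAP is silent on timing and does not say that.
- **The repeated-measures models are not a contradiction.** Each adjusts for the baseline value of its own outcome, and a day count has no such value. This stands: they show that the covariate is available and acceptable to the authors, not that the SAP conflicts with itself.
- **The gain is not uniform.** A reader might carry the upper ventilator-day figures over to all four counts. The documents give no basis for that, and the figures for hospital and oxygen days are probably smaller.
- **Four of the six comparisons are a second look.** ICU and hospital stay, actual and medical equivalence, are also tested by Gray's test. This stands and narrows the point to ventilation and oxygen days, for which the ANOVA is the only comparison.
- **The trial is exploratory and states no power target.** This limits the importance, but it does not argue against using data already collected.

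**Conclusion.** The point holds as a minor precision improvement to secondary endpoints. The default model omits a predictor that is recorded before randomisation, varies because eligibility allows it to, and is not described as a stratification factor. The optional ANCOVA leaves the planned model undetermined.

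The likely gain is equivalent to about 3-50% more subjects for ventilator days and about 3-20% for hospital and oxygen days. Both ranges rest wholly on assumed baseline mix, mortality and durations. ICU days were not simulated. The primary mortality analysis is unaffected, and nothing here shows that a conclusion of the trial would change.

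**What to change.** In SAP 6.2, replace the ANOVA and its optional ANCOVA with a prespecified ANCOVA for all duration endpoints. The terms are treatment, baseline Ordinal category (for ventilator days, invasive ventilation at randomisation yes/no), age and gender. Gender stays because the SAP already names it here and in the repeated-measures models. Keep the unadjusted ANOVA as a supportive analysis.

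The change is to SAP wording only and needs no new data. About 100 subjects and a treatment-only model leave 100 − 2 = 98 error degrees of freedom. Inclusion 3b implies three Ordinal categories at entry (2, 3 and 4), which cost two degrees of freedom, and age and gender cost one each, leaving about 94 (about 95 for ventilator days).
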